The current IMDs guidelines are cautious about the recommendations on the use of CGM and its clinical practice application in nutritional improvements or modifications (15–17). Rossi et al. have recently proposed indications for CGM monitoring and CGM outcome parameters in patients with hepatic GSDs (14). Peeks et al. also indicated outcome parameters for hepatic GSDs (13).

Worth et al. have recently analyzed the state of art of the evidence for the use of CGM in non-diabetic children with hypoglycemia (9). Some suggestions for qualified CGM use have been provided, but a focus on patients' perspectives on the use of different CGM systems is still lacking, especially on recent tools developed by new technologies.

Study Objectives

Primary objective

Assessment of Pre-set targeted time in hypoglycemia and number of episodes of pre-set hypoglycemia during the different periods of use of CGM tools based on different alarms.

Secondary objectives

Accuracy of the two different CGM systems (comparator SBGM by capillary finger stick).

Assessment of patients' perspectives and tolerance to the use of two subsequent different CGM systems and tools, in particular on different types of alarms: Dexcom One Plus (Dexcom) with threshold alarm and Dexcom G7 (Dexcom) with predictive alarm.

Assessment of quality of life and sleep quality.

Assessment and comparison of glycemic control, patients' perspective and tolerance of CGM with USUAL Care CGM.

Study Design

Study Type

Prospective interventional with medical devices CE

Study Site

Sample Size Estimation

11 IMDs at risk for hypoglycemia

The rare condition of disorders investigated needs to be considered for the sample size (e.g. GSD I has a frequency of approximately 1 in 100,000 and the estimated incidence of CHI ranges between 1:27,000 and 1:50,000 live births in outbred western population).

Randomization

Patients will be randomized to start with the use of Dexcom G7 o Dexcom One Plus after baseline.

Methods for randomization: Randomization will be employed to assign participants to different

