Statistical Analysis (example)

(1) General Principles

Quantitative variable will be described by the total number of cases, number of missing values, mean, and standard deviation, minimum, maximum and median. Categorical variables will be described by the number of cases and percentages.

All statistical tests will be performed using two-sided test, P value less than or equal to 0.05 will be considered to have examined the difference statistically significant (Unless otherwise noted). For comparison between two groups of the general condition, the suitable method shall be adopted to conduct analysis according to the type of indicators; for the comparison among groups of quantitative data, group t test (homogeneity of variance, normal distribution) or Wilcoxon rank-sum test will be adopted according to the data distribution (the Shapiro-Wilk test will be used beforehand to check whether the variables follow a normal distribution or not); for categorical data, the chi-square test or Fisher's exact test (if the chi-square test is not applicable) shall be adopted; for ordered data, Wilcoxon rank-sum test or Cochran-Mantel-Hansel test shall be adopted. Multiple regression analyses will also be considered, including linear regression for continuous dependent variables, Poisson regression and cumulative logit logistic regression for ordered response variables (or logistic regression for dichotomous variables, such as presence/absence). Moreover, ANOVA or mixed-effects models will be used to compare how the effect of interest varies over time within the same subject, repeated measures.

(2) Completion and Baseline Parameters

The summary of the study completion includes the count of completed cases of each study center, the list of dropout cases, the analysis set description, the comparison of dropout rates of the groups and the list of reasons for incompleteness. The summary of baseline parameters includes demographic characteristics (gender, age, height, vital signs etc.), history of illness and medications, and specific Questionnaires about CGM tolerance, perspectives and expectations. Comparisons among the two different CGM devices groups and gold standard by capillary finger stick will be conducted to evaluate MARD and reliability during the period of observation.

(3) Compliance

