- Compliance of study: study compliance to the CGM two medical devices and capillary finger sticks of all groups will be described and compared. A list of subjects with poor compliance (80% below or 120% above compliance) will be generated.

Observation parameters list (CRF)

Patients at screening, baseline, after 30 days of **unblinded monitoring** with Dexcom G7 and 30 days of **unblinded monitoring** with Dexcom One Plus (Fig. 2). The start of the single CGM tool will be randomized (i.e. 50% of patients will random start with G7 and then switch to Dexcom One Plus, and *viceversa*).

- 1) SCREENING _ General data collection: age, gender, height, body weight, minority, career, income, degree of education, family history, smoking habit, primary diseases or accompanied diseases.
- 2) SCREENING _ Previous glucose monitoring (referring to the last 8 weeks): number of capillary fingers sticks per day, use (or not) of CGM and type of CGM device
- 3) SCREENING _ Major comorbidities
- 4) SCREENING _ Document intake of medications
- 5) SCREENING _ Adverse events and the rate of hospitalization during the last year
- 6) BASELINE _ Quality of Life (SF-12 rating scale)
- 7) BASELINE _ Quality of Sleep (Pittsburgh sleep quality index (PSQI))
- 8) FOLLOW UP _ Capillary finger sticks glucose values (3 per day) by diary record

- 9) FOLLOW UP_ CGM values: time above, under or in the pre-set target, number of episodes of pre-set hypoglycemia
- 10) FOLLOW UP_ CGM tolerance, perspectives and expectations (Specific questionnaires)
- 11) FOLLOW UP_ CGM Quality of Sleep (Pittsburgh sleep quality index (PSQI), quality of life (SF12))
- 12) FOLLOW-UP_ Education on the use of CGM device (sensor, receiver or other tools)

Flowchart indicating which parameter is measured when:

Observation Parameters	Screening	Enrollment/Baseline	Follow up - After 30 days	Final Visit study - After 30 days
Informed consent	x			
Demographic (Age, Gender, Career, Degree of Education, Income)	x			
Height	x			
Body Weight	x	x	x	x
Family History	x			
Smoking Habit	x			
Physical exam	x			
Vital signs	x			
Primary Diseases or Accompanied Diseases	x			
Major IMD Comorbidities	x			
Glucometer values		x	x	x
Use of CGM	x			
Documented Intake of Medications	x			
Rate of Hospitalization During the Last Year	x			
Type of CGM Device	x	x	x	x
Capillary finger sticks glucose values (3 per day)		x	x	x
CGM values (time in pre-set hypoglycemia, number of pre-set hypoglycemia, MARD)		x	x	x

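### The stated test for comparing the two devices on MARD assumes independent samples, although both device groups are the same 11 patients and no unit of analysis is given

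*Combined protocol and SAP*

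**What the plan says.** Under Statistical Analysis, (2) Completion and Baseline Parameters, the plan states: "Comparisons among the two different CGM devices groups and gold standard by capillary finger stick will be conducted to evaluate MARD and reliability". It names no test, unit of analysis or interval method there.

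The rule for quantitative data is in (1) General Principles: "for the comparison among groups of quantitative data, group t test (homogeneity of variance, normal distribution) or Wilcoxon rank-sum test will be adopted". The same paragraph ends by allowing ANOVA or mixed-effects models for repeated measures, described as a way to see how an effect changes over time within a subject. That sentence does not mention MARD, finger-stick pairs, sensors or the contrast between devices.

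The design is a crossover. The Observation parameters list (CRF) gives 30 days on each device in randomized order: "50% of patients will random start with G7 and then switch to Dexcom One Plus", and the reverse for the rest. Item 8 of that list sets the reference measurements: "Capillary finger sticks glucose values (3 per day) by diary record". The Sample Size Estimation section reads "11 IMDs at risk for hypoglycemia". Accuracy and MARD are listed as secondary under Endpoints.

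**The concern.** A group t test and a rank-sum test both compare two sets of independent observations. Here the two sets come from the same people, and each person contributes many readings. Readings from one patient, and from one sensor, are likely to resemble each other.

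The plan's rule could be applied in two ways, and the text does not choose between them. An analyst could pool the absolute relative differences of all finger-stick pairs, which ignores the clustering. Or an analyst could take one MARD per patient per device and compare the two sets of 11 values as if they came from different people, which discards the pairing that the crossover provides. At stake are the precision claimed for each device's accuracy and the validity or sensitivity of the comparison between devices.

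**Working it through.** **No figure to reproduce.** The sample size of 11 is justified by rarity alone. The plan gives no MARD precision, standard deviation or effect size.

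**Inputs from the documents.** 11 patients; 30 days per device; 3 finger sticks per day; two-sided test at 0.05.

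**Assumptions.** The documents give no variance shares, so all are assumed. Total variance of one pair's absolute relative difference is set to 1 and split into v_p (patient, shared by both devices), v_pd (patient-by-device), v_s (sensor) and v_e (residual). Three sensors per period are assumed, so 30 pairs per sensor.

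**Step 1: number of pairs.** 11 × 30 × 3 = 990 per device if every finger stick has a matching CGM value. Across the 80% to 120% compliance band of the per-protocol set this is 792 to 1188.

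**Step 2: interval for one device, pairs pooled.** Each patient gives 90 pairs, so the design effect is 1 + 89 × ICC.

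| ICC | Design effect | Effective pairs | Correct interval wider by | Actual coverage of nominal 95% |
|---|---|---|---|---|
| 0.01 | 1.89 | 524 | 1.37 | 85% |
| 0.05 | 5.45 | 182 | 2.33 | 60% |
| 0.10 | 9.90 | 100 | 3.15 | 47% |

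The direction is the same for every positive ICC.

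**Step 3: device test, pairs pooled.** The variance that the unpaired test assumes for the difference is 2/990. The true variance is 2 × (v_pd/11 + v_s/33 + v_e/990). Their ratio is R = 90 v_pd + 30 v_s + v_e, and the type I error is 2 × (1 − Φ(1.96/√R)).

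- Shared patient effect only, v_p = 0.05, 0.10 or 0.20: R = 0.95, 0.90 or 0.80; type I error 4.4%, 3.9% or 2.8%. The shared effect cancels and the test is slightly conservative.
- v_p = 0.05 with v_s = 0.02, 0.05 or 0.10: R = 0.60 + 0.93 = 1.53, 1.50 + 0.90 = 2.40, or 3.00 + 0.85 = 3.85; type I error about 11%, 21% or 32%.
- v_p = 0.05 with v_pd = 0.01, 0.02 or 0.05: R = 0.90 + 0.94 = 1.84, 1.80 + 0.93 = 2.73, or 4.50 + 0.90 = 5.40; type I error about 15%, 24% or 40%.

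With no sensor variance, R exceeds 1 once v_pd is above v_p/89, about 1.1% of the shared patient variance. Simulation with normal errors agrees with these values. For example, the pooled t test rejected 4.2% with the shared effect alone and 19.8% at v_s = 0.05. The rank-sum test behaved almost identically.

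**Step 4: device test on one MARD per patient per device, unpaired.** Let q = v_pd + v_s/3 + v_e/90. The true variance of the difference is a fraction k = q/(v_p + q) of what the unpaired test assumes. With v_p = 0.05:

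- no other clustering: q = 0.95/90 = 0.0106, k = 0.0106/0.0606 = 0.17
- v_s = 0.05: q = 0.0167 + 0.0100 = 0.0267, k = 0.0267/0.0767 = 0.35
- v_s = 0.10: q = 0.0333 + 0.0094 = 0.0428 (before rounding), k = 0.0428/0.0928 = 0.46
- v_pd = 0.05: q = 0.0500 + 0.0100 = 0.0600, k = 0.0600/0.1100 = 0.55

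In eight simulated scenarios (v_p of 0.05 or 0.10, 3,000 trials each) the unpaired t and rank-sum tests rejected a true null 0% to 1.3% of the time. A further simulation (3,000 trials per scenario) set the true difference at 0.94 standard deviations of the within-patient difference, where the paired t test has 80% power. In the four cases above the unpaired t test had about 10%, 39%, 53% and 60% power.

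**Step 5: paired analysis.** The paired t test on the 11 within-patient differences rejected a true null 4.4% to 5.2% of the time in the same eight scenarios.

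**The case against.** The strongest reply is that the plan never says pairs are pooled. The flowchart in the Observation parameters list puts MARD in one row with time in hypoglycemia and number of episodes, both per-patient summaries recorded at visits. On that reading there are 11 values per device, and the error is lost power rather than false positives. This stands. A reader might infer that 990 readings will be treated as independent and that false device differences will be too frequent. The documents do not support that as a statement of fact. Even under pooling, inflation needs sensor-level or patient-by-device variance, and its size cannot be taken from the documents.

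Second, the plan proposes no confidence interval for MARD; its descriptive summaries are mean, standard deviation, median and range. This also stands, so Step 2 applies to any interval that might be reported from pooled pairs, not to one the plan has promised.

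Third, the repeated-measures sentence could be stretched to cover two devices used in successive periods, the t-test sentence opens with wording that could be read as being about baseline characteristics, and the section is labelled as an example. This stands only in part. The MARD sentence calls the devices groups, and the rule for comparing quantitative data among groups is an independent-samples test. The mixed-model sentence is about change over time and is not tied to the device contrast. An analyst could follow the text and run a rank-sum test.

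**Conclusion.** The point holds as a mismatch between the stated test and the design, together with a missing unit of analysis. It does not hold as a claim that the trial will report too many false device differences.

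The direction of error depends on the unit. Pooled pairs give intervals that are too narrow for any positive ICC. They give a device test anywhere from slightly conservative (2.8% to 4.4%) to clearly inflated (11% to 32% for sensor shares of 0.02 to 0.10, up to 40% for a patient-by-device share of 0.05). Patient-level values analysed as unpaired give a strongly conservative test and a substantial loss of power. That second result needs a shared patient effect; were there none, the unpaired patient-level test would hold its level.

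All variance shares, and the three sensors per period, are assumptions. The existence of the mismatch does not depend on them; the sizes do. MARD is a secondary endpoint, so the primary result is untouched. The plan should be changed, but this is not a reason to doubt the main comparison.

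**What to change.** State in the Statistical Analysis section that the patient is the unit for MARD. Compute MARD and signed bias per patient and device, and compare devices by the within-patient difference, with a paired test or a model that also includes period. Period matters because 11 patients cannot be split equally between the two orders. Alternatively, fit a mixed model to the pair-level data with patient, patient-by-device or sensor, and period effects. Report each device's MARD with an interval clustered on patient, for example one based on the 11 patient-level values or on resampling patients.

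The cost is wording, plus a less favourable but correct stated precision for each device's MARD. If a sensor term is used, each pair must be labelled with its sensor, which the CRF list does not mention; the patient-level paired analysis needs no additional data.

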Study Population Major Selection Criteria:	Adults affected by Glycogen Storage Disorders and Congenital Hyperinsulinism >18 years; Genetic or biochemical diagnosis of Glycogen Storage Disorder or Congenital Hyperinsulinism, in regular clinical follow up at outpatient services.
Estimated total number of subjects	11
Study Duration	First patient in: 01/01/2025 Last patient out: 01/08/2025

Study Background

Inherited metabolic disorders (IMDs) at risk for hypoglycemia include some rare disorders of intermediary metabolism and metabolic cell signaling (1). Among disorders of intermediary metabolism, Glycogen Storage Disorders (GSDs) are the most relevant, while among metabolic cell signaling congenital hyperinsulinism (CH) is the most frequent.

GSDs are a group of monogenic defects in the synthesis or breakdown of glycogen, with prevalent hepatic and/or muscle involvement, as glycogen is particularly abundant in these tissues (2). The overall estimated incidence of GSDs is 1 case per 20,000-43,000 live births, with over 20 types, including subtypes, and a wide spectrum of clinical presentation (2,3). The management of GSDs is based on dietary treatment, with the goal of maintaining glucose homeostasis and preventing long-term complications; organ transplantation may be an option in some patients (2,3). CH is the most frequent cause of persistent hypoglycemia in pediatric patients. In CH, mutations in 12 different key genes cause inappropriate insulin secretion by pancreatic β -cells, resulting in persistent hypoglycemia (4,5). Moreover, suppressing lipogenesis and ketone body formation during hypoglycemia, CH leads to a higher risk of brain injury. Long-term management in CH involves a combination of pharmacologic therapies and, in cases unresponsive to medical treatments, surgical interventions that may include up to subtotal pancreatectomy (removal of 95–98% of the pancreas) (4). Nutritional management includes frequent feeding with high-caloric carbohydrate feeds, UCCS, and sometimes enteral tube feeding (24/24h or only during the night) (5,6).

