In IMDs at risk for hypoglycemia subjects have to control their blood glucose levels to evaluate treatment efficacy. Blood glucose check could be performed through self-monitoring blood glucose (SMBG) by finger stick or through continuous monitoring of glucose concentrations in the subcutaneous tissue. In subjects with type 1 diabetes mellitus (T1DM), Continuous Glucose Monitoring (CGM) is considered a primary standard of care, as it has been shown to improve glycemic control and reduce the frequency of hypoglycemia (7,8). CGM avoids the distress and burden of multiple blood capillary measurements per day; it can also detect glycemic patterns and asymptomatic or overnight hypoglycemia by analyzing recorded glucose level data. Trend arrows suggest future glucose patterns and alarms help in preventing hypo and hyperglycemia (9). In patients with T1DM, glycemic targets have been defined for CGM-parameters (i.e., time in range (TIR) and time above (TAR) and below (TBR) range, glucose variability expressed by coefficient of variation (CV)), and the percentage of TIR has been included in the standard set of person-centered outcomes (10,11).

CGM devices have been divided into two classes based on their characteristics: Real-time CGM (Rt-CGM) and intermittent scanned CGM or Flash Glucose Monitoring (FGM). Rt-CGM gives users the possibility to visualize data in real time on a receiver or smartphone app and it is equipped with alarms (threshold, predictive, or related to arrow trend). FGM reports the user's glucose values when the sensor is scanned by a reader or smartphone app. The first FGM version has not been equipped with alarms, while the second version has been equipped with threshold alarms. Then, the latest FGM version of the App can display real time glucose values.

The actual differences in Rt-CGM systems are in costs, possibility to silence the alarms, number of alarms during the day, selection of pre-set targets, possibility of setting additional alerts, time of sensor duration, only use of smartphone or use of specific receiver.

The role and outcomes of CGM in patients with IMDs at risk of hypoglycemia are still debated by researchers and clinicians expert in the field (9,12–14). However, as CGM has been shown valuable in patients with T1DM to detect unrecognized hypoglycemia and monitor individual glycemic variability (GV), its potential benefit for patients with IMDs is high.

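### Medication is recorded only at screening and diet at no visit, so regimen changes prompted by the first device and carried into the second period cannot be detected or adjusted for

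*Combined protocol and SAP*

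**What the plan says.** **What is recorded.** The Observation parameters list (CRF) has one medication item, "SCREENING _ Document intake of medications". In the flowchart the row "Documented Intake of Medications" is ticked in the screening column and nowhere else. None of the 12 list items and no flowchart row covers diet, cornstarch or feeding. The only diary is for glucose: "Capillary finger sticks glucose values (3 per day) by diary record". Body weight, at best an indirect nutritional marker, is ticked at all four visits.

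**Why these variables matter, by the protocol's own account.** The Study Background says of GSD: "The management of GSDs is based on dietary treatment, with the goal of maintaining glucose homeostasis". Of congenital hyperinsulinism it says "Long-term management in CH involves a combination of pharmacologic therapies" and "Nutritional management includes frequent feeding with high-caloric carbohydrate feeds, UCCS, and sometimes enteral tube feeding". It adds that in these disorders "subjects have to control their blood glucose levels to evaluate treatment efficacy".

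**Design and analysis.** Eleven patients use both devices for 30 unblinded days each, in randomized order. Randomization is simple, with blocking optional. The Statistical Analysis section allows ANOVA or mixed-effects models for repeated measures, but names no period, sequence or carry-over term and no covariate for treatment change. No text requires a stable regimen or describes a washout. Figure 2 is not visible, so the absence of a washout is judged from the text alone.

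**The concern.** Patients see their glucose data throughout, and the background presents glucose checks as the means of judging treatment. It is therefore plausible that some patients or clinicians will adjust feeds or drugs after seeing the first device's data. The documents do not say that this will happen, and no treatment review is listed at day 30. They do not rule it out either.

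A change that persists into the second period affects glucose while the other device is worn. If the two devices prompt such changes to different degrees, the second-period values carry a trace of the first device, and the comparison of hypoglycemia between devices is biased. With nothing recorded after screening, the trial could not report how many changes occurred, on which device or in which period, and could not examine their influence.

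A second comparison is more exposed. One secondary objective sets glycemic control on the study devices against usual-care CGM, which is not a randomized arm. The flowchart collects CGM values at baseline and at both later visits. If the comparison is before-after, an unrecorded regimen change falls directly into it.

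**Working it through.** The plan has no figure to reproduce. The sample size of 11 is justified by rarity, without effect size, SD or power. The check is therefore what a regimen change does to the device contrast in a two-period crossover.

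**Notation (effects are assumed; none is in the documents).** τ is the true difference A − B. π is a shift in period 2 common to all patients. λ_A and λ_B are the effects in period 2 of regimen changes prompted by A or B in period 1. Negative values mean less hypoglycemia.

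**Expected A − B difference by sequence.**
- A first: τ − π − λ_A
- B first: τ + π + λ_B

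**Period-adjusted estimate.** This is the mean of the two sequence means, τ + (λ_B − λ_A)/2. The common shift π cancels; half the difference in carried effects remains.

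**Case 1: a change common to both sequences.**
- With a period term the bias is 0. Simulation with 20,000 runs and a shift of −1 gave −0.003 at a 6/5 split and +0.002 at 8/3.
- Without a period term the bias is the shift × |n_AB − n_BA|/11: 1/11 = 9% of the shift at 6/5, 3/11 = 27% at 7/4, 5/11 = 45% at 8/3.
- Under simple randomization of 11, the probability of a 6/5 split is 924/2048 = 0.451, and of 8/3 or worse 464/2048 = 0.227.

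**Case 2: a change that depends on the first device.** Take λ_A = −1 and λ_B = −0.5 in within-period SD units, with τ = 0.
- Period-adjusted: (−0.5 + 1)/2 = 0.25 at any split (simulated 0.247 at 6/5, 0.255 at 8/3).
- Unadjusted: (6 × 1 − 5 × 0.5)/11 = 0.32 at 6/5, and (8 × 1 − 3 × 0.5)/11 = 0.59 at 8/3.
- Range of the adjusted bias: 0 if the carried effects are equal, 0.25 if they differ by 0.5 SD, 0.5 if they differ by 1 SD.

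The positive sign here means that A, the device that prompted the larger lasting improvement, looks worse, because the benefit is credited to B.

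**Case 3: a few patients change, unrelated to sequence.** Assume that a day-30 change lowers one patient's time below 70 mg/dL from 6% to 3%.
- Unadjusted mean difference: 3/11 = 0.27 points for one patient, 9/11 = 0.82 for three in the same sequence.
- Period-adjusted at 6/5: 3/(2 × 6) = 0.25 or 3/(2 × 5) = 0.30 for one patient; 0.75 or 0.90 for three.
- Probability that three changers share a sequence: 2 × (1/2)³ = 0.25 under simple randomization, or (20 + 10)/165 = 0.18 at 6/5. A 2–1 division gives a net unadjusted shift of 0.27.

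These are single possible draws. Averaged over randomization they add variance, not bias.

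**The case against.** The strongest reply is that the design already handles most of this. Order is randomized and each patient is their own control, so a regimen change unrelated to which device came first favours neither device in expectation. A reader might infer from the missing records that treatment changes cannot be separated from the device effect at all. The documents do not support that: Case 1 is removable with a period term, and Case 3 is noise that the standard error reflects. The 0.27 to 0.82 points should not be read as bias.

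A second reply is that a change made within a period in response to that period's device may be part of the device's effect. The background credits alarms and trend arrows with helping to prevent hypoglycemia, and the plan does not say whether the intended effect includes such responses. This also stands, and it confines the concern to what is carried into the next period.

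Neither reply meets Case 2. Randomizing the order does not remove unequal carry-over. A sequence term does not remove it either: the sequence comparison mixes carry-over with differences between patients, here in only 11 patients. The protection in Case 1 also depends on a period term that the plan does not name. A washout, if Figure 2 shows one, would not undo a lasting regimen change. The content of the CGM questionnaires is not given, so they cannot be assumed to capture regimen changes.

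**Conclusion.** The gap in data collection is certain on the text: medication is recorded once, before either device is worn, and diet never. The consequence is narrower than general confounding. Regimen changes prompted by the first device and carried into period 2 cannot be detected, described or adjusted for, and they bias even a period-adjusted contrast by half the difference in carried effects. That difference is unknown. It is zero if both devices prompt the same lasting changes, and the 0.25 and 0.5 SD figures rest on assumed differences. The plan's silence on a period term adds a second, avoidable exposure when the sequences are unequal in size.

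For the comparison with usual-care CGM, the conclusion is conditional: if it is before-after, neither randomization nor a period term protects it. The documents do not say how that comparison will be made.

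**What to change.** - **Record.** Tick the existing medication row at baseline, day 30 and day 60 as well. Add a row for the current dietary regimen (UCCS, feeding schedule, tube feeding) at the same three visits. For any change in either, record the date, the reason and whether CGM data prompted it.
- **Report.** Give the number of changes by device, period and sequence.
- **Primary analysis.** Keep all patients and all data, and name period and sequence terms in the mixed model.
- **Sensitivity analysis.** Fit a model with a regimen-change indicator, labelled exploratory because a within-period change may be part of the device's effect. Do not drop glucose data after a recorded change. That would condition on a post-randomization event the device may have caused, and for a change at day 30 it would remove the patient's whole second period.
- **Missing data.** State that LOCF, which the full analysis set definition applies to missing primary outcomes, is not used across periods. Carrying a period-1 value into period 2 forces that patient's device difference to zero.

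The cost is two CRF rows at three existing visits, a few minutes of interview each time, and a protocol amendment through the Ethics Committee. Patient care does not change; whether regimens may be altered during the study remains the investigators' decision.
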